4.4.4 General Anxiety Disorder-7

• Change from baseline in GAD-7 total score over time

The GAD-7 is a 7-item instrument that quantifies the symptom severity in generalized anxiety disorder in the last 2 weeks (Spitzer et al, 2006) and is collected during screening, at week 4 and at week 12/EoT. Concepts assessed are the frequency of being anxious, worried, having troubles relaxing, being restless, annoyed or irritated and feeling afraid. The items are scored on a 4-point Likert scale from 0 to 3 (0 = not at all, 1 = several days, 2 = more than half the days, 3 = nearly every day). The scores are summed to produce the total score (maximum of 21), with higher scores indicating a higher frequency of anxiety symptoms.

The total score can be categorized into the below level of anxiety severity:

- 0-4 = None/minimal anxiety
- 5-9 = Mild anxiety
- 10–14 = Moderate anxiety
- 15–21 = Severe anxiety

The item 'If you checked of any problems, how difficult have these problems made it for you to do your work, take care of things at home, or get along with other people?' from the PHQ-9 is also assessed as part of the GAD-7 form on the ePRO device. Participants respond using a 4-point response scale 'Not difficult at all' to 'Extremely difficult'.

The absolute values and change from baseline values for GAD-7 total score will be summarized using descriptive statistics by study treatment and week. The baseline value will be the earliest assessment on day 1 or day 2. If both day 1 and day 2 assessment is not available, the baseline value will be the latest available assessment on or before day 4. Only assessments where ≥ 8 days of the 14-day recall period are outside of the impact duration of prohibited hormonal therapies and medication potentially confounding efficacy will be included. Details regarding the prohibited medications together with the impact duration are described in Section 6.3. The change from baseline over time by study treatment will be shown using line plots for means and 95% CI.

The GAD-7 anxiety severity categories will be summarized using frequency tables by study treatment and week. Stacked bar charts showing the composition of anxiety levels at each week by treatment group will be produced.

In addition, the number and percentage of each response for each individual item, as well as the item from PHQ-9, will be summarized using frequency tables by study treatment and week. Stacked bar charts will also be produced showing the composition of responses for each item by treatment group and week.

4.4.5 Patient Global Impression of Severity (PGI-S) and Change (PGI-C)

- Change from baseline in PGI-S individual item scores over time
- Absolute values of the PGI-C individual item scores over time

Version 2.0 Page: 34 of 57

The PGI-S includes 2 items assessing sleep problems over the past week using a 5-point response scale ("No sleep problems" to "Very severe" for the PGI-S item 1 (severity of sleep problems) and "None of the time" to "Nearly all of the time" for PGI-S item 2 (time spent awake after first falling asleep)). Each item is answered independently.

The PGI-C includes 2 items assessing change in sleep problems since the participant started taking the study medication. A 5-point response scale is used ranging from "much better" to "much worse" for PGI-C item 1 (change in severity of sleep problems) and "much less" to "much more" for PGI-C item 2 (change in time spent awake). Each item is answered independently.

Both instruments, the PGI-S and the PGI-C are self-invented by the sponsor strongly following regulatory guidance (FDA 2018) and are collected weekly as per the SOA in the protocol (Section 1.3 of protocol). Weekly and EoT assessments will be assigned to study week using the same mapping as PROMIS (see Section 4.3.2.1), i.e., accounting for the recall period of 7 days, and the impact duration of prohibited hormonal therapies and medication potentially confounding efficacy for baseline derivation. If more than one assessment is assigned to a week, e.g., participant completes a weekly assessment and very shortly has a protocol scheduled visit (including EoT), the latest available assessment will be used in the analysis.

The answers to the 2 individual items for PGI-C and PGI-S will be summarized in frequency tables by study treatment and week. The change from baseline in PGI-S individual scores will also be analyzed using shift tables (observed frequencies at baseline versus post-baseline weeks).

4.5 Safety Analyses

The analyses described in this section will be presented for the SAF.

4.5.1 Extent of Exposure

Treatment duration will be defined as the number of days from the day of first study intervention intake up to and including the day of last study intervention intake and will be summarized using descriptive statistics by study treatment. Treatment duration will be presented based on the data collected via the eCRF. If the date for end of exposure is not available in eCRF, the last day of intervention intake from eDiary will be used to determine the end of exposure.

The compliance (as percentage) will be calculated as:

100 * Number of capsules taken / Number of planned capsules

The number of planned tablets is calculated as:

Treatment duration * 2

All capsules, including the placebo capsules, will be counted. For participants who withdraw prematurely from the study treatment, compliance will be calculated up to the time of last dose. The compliance will be summarized descriptively by study treatment. In addition, percent of compliance will be categorized into 3 groups, <80%, 80 to 120% >120%, and the categories will be summarized by study treatment.

Version 2.0 Page: 35 of 57

Compliance will be calculated and presented twice, once based on the ePRO daily instrument 'Study medication intake documentation' and once based on the eCRF 'Drug Accountability' and 'Study Intervention' pages. If the 'Study medication intake documentation' on the second PSG night at week 12/EoT is missing but the last treatment intake on the eCRF 'Study intervention' pages indicate that the participant took treatment on the night, the 'Number of study medication capsules taken' on the 'Study medication intake documentation' will be imputed with 1 capsule.

The summaries for treatment duration and compliance will be presented for the overall intervention period, (i.e., 12 weeks).

4.5.2 Adverse Events (AEs)

All AEs will be summarized using MedDRA (the current version at the time of analysis) PTs grouped by SOC.

Any AEs related to study procedures recorded after signing of informed consent but prior to randomization will be considered as pre-treatment AEs. AEs that occurred or worsened after the first dose of study intervention up to 14 days after the last dose of study intervention will be considered as treatment-emergent AEs (TEAEs). AEs that occurred 15 days after last dose will be considered as post-treatment AEs.

Partially missing onset AE date will be imputed following a worst-case approach as described in Section 4.1.1.4.

If the severity of a previously reported event worsens or if the relationship to study intervention/protocol required procedures changes, two separate events should be reported.

Worsening of an AE is defined as follows:

- AE intensity is worsened (e.g., moderate to severe)
- AE changed to a serious event
- AE ends with death

In case an AE starts before the date of last study intervention intake + 14 days and worsens after last study intervention intake +14 days, it will be considered as two AEs, a TEAE and a post-treatment AE.

In case of events with different intensity within a participant, the maximum reported intensity will be used. If the same event is reported as both unrelated and related to the study intervention within a participant, the event will be considered as related to study intervention. If the study intervention relationship is missing, the event will be considered as being related to the study intervention. For AEs, relationship to study intervention refers to elinzanetant and placebo only.

Overall summaries of the number of participants with pre-treatment AEs, TEAEs, and post-treatment AEs will be generated by study treatment.

The number of participants with the following AEs will be summarized by study treatment using PTs grouped by SOC:

- pre-treatment AEs
- post-treatment AEs

Version 2.0 Page: 36 of 57

- SAEs (includes both treatment-emergent and post-treatment)
- TEAEs, TEAEs of special interest, TEAEs resulting in discontinuation of study intervention, TEAEs by maximum intensity
- treatment-emergent study intervention related AEs, treatment-emergent study intervention-related AEs by maximum intensity, treatment-emergent study intervention-related AEs resulting in discontinuation of study intervention
- treatment-emergent SAEs, treatment-emergent SAEs of special interest, treatmentemergent SAEs resulting in discontinuation of study intervention, treatment-emergent SAEs by maximum intensity, treatment-emergent study intervention-related SAEs, treatment-emergent study intervention-related SAEs by maximum intensity
- AEs with fatal outcome (includes both treatment-emergent and post-treatment), TEAEs with fatal outcome

Listings of treatment-emergent SAEs, and AEs with fatal outcome will be provided.

Adverse events of special interest (AESI)

The following are defined as AESI in this study, if the event takes place after the first intake of study intervention:

- 1. Any condition triggering close liver observation (as listed in Protocol Section 8.4.6): identified by Standardized MedDRA Query (SMQ) searches and AESI 'tick-box' via eCRF
- 2. Post-menopausal bleeding: identified by MedDRA Labeling Grouping (MLG) and PT searches

See details in Section 6.5 for SMQ, PT and MLG search criteria.

4.5.3 Additional Safety Assessments

For laboratory, liver monitoring, and vital signs the number of participants whose baseline value is a measurement while taking or washing-out prohibited hormonal therapies or medications potentially confounding efficacy during the screening period will be reported in a table.

4.5.3.1 Laboratory Data

The number of participants with treatment-emergent (i.e., 14 days from the last treatment intake) high or low abnormal laboratory values will be summarized for each laboratory parameter by study treatment. Both scheduled and unscheduled laboratory measurements will be considered.

Continuous laboratory parameter values including the change from baseline will be summarized by visit and study treatment. Frequency tables for categorical laboratory parameter will be summarized by visit and study treatment.

Central laboratory will be considered for descriptive analysis. Local laboratory measurements will be listed, if available.

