2 E.g., for US: Normal breast cancer screening result must be documented no more than 9 months prior to start of treatment.

21 SEP 2023 Page: 26 of 73

5.2 **Exclusion Criteria**

Participants are excluded from the study if any of the following criteria apply:

Medical Conditions

- 1. Medical history, or baseline PSG assessment, includes a diagnosis of a sleep disorder other than sleep disturbances associated with the menopause (e.g., sleep apnea, restless leg syndrome, circadian rhythm sleep disorder).³
- 2. Clinically significant abnormalities that interfere with the study goals, in the opinion of the investigator, based on the medical history, physical examination, vital signs, clinical laboratory tests⁴, eC-SSRS, and other assessments completed during screening.
- 3. Current or history (except complete remission for 5 years or more) of any malignancy (except basal and squamous cell skin tumors).
- 4. Renal impairment greater than moderate (i.e. estimated glomerular filtration rate <30 mL/min/1.73 m²) at screening.
- 5. Abnormal liver parameters (presence of at least one of the following criteria):
 - $AST > 2 \times ULN$
 - ALT >2 x ULN
 - AP >2 x ULN
 - TBL >ULN unless explained by Gilbert's syndrome
 - INR >ULN unless explained by, e.g., intake of anticoagulants⁵
 - Diagnosis of hepatitis B infection, i.e., Hbs-antigen positive at screening
 - Diagnosis of hepatitis C infection, i.e., hepatitis C antibodies and HCV-RNA positive at screening.

Prior/Concomitant Therapy

- 6. Has used and is unwilling to wash-out use of any of the prohibited concomitant medications, as specified in Sections 6.9 and 10.7.
- 7. Inability to comply with the use of prohibited medications as described in Sections 6.9.1 and 10.7.
- 8. Current cognitive behavioral therapy for sleep disorders.

Prior/Concurrent Clinical Study Experience

9. Concurrent (or within 2 months prior to signing of ICF) participation in a clinical study with an investigational medicinal product (including medical devices) with the exception for participants who completed another elinzanetant study.

⁴ Single re-test allowed.

⁵ Re-test of INR will be allowed once.

³ Details are provided in the PSG manual.

21 SEP 2023 Page: 27 of 73

Other Exclusion Criteria

- 10. Shift work within 2 weeks prior to the SCR-2 visit, or planned shift work during the study.
- 11. AHI >15 on the first PSG screening night.
- 12. PLMAI > 15 on the first PSG screening night.

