1.1 Objectives, Endpoints, and Estimands

Objectives and endpoints are listed in Table 1-1.

Table 1-1: Objectives and Endpoints

Objectives	Endpoints
Primary	
To explore the efficacy of elinzanetant on sleep disturbances associated with menopause as determined by PSG	Primary endpoint Change from baseline in WASO at week 4 as measured by PSG Secondary endpoints Change from baseline in WASO at Week 12 as measured by PSG Change from baseline in SE at week 4 as measured by PSG Change from baseline in SE at week 12 as measured by PSG Change from baseline in SE at week 12 as measured by PSG Exploratory endpoints Change from baseline at week 4 and week 12 in PSG measures of sleep onset, duration, and continuity: LPS, TST, SOL, SOLN1, WTDS, EMWT, TWT, NAW, mean duration of awakenings, WASO each quarter of the night Change from baseline at week 4 and week 12 in PSG measures of different sleep stage durations: time and percent in stage N1 sleep, time and percent in stage N2 sleep, time and percent in non-REM sleep, time and percent in REM sleep, REM onset latency from sleep onset Change from baseline at week 4 and week 12 in other PSG measures: arousal index
	and number of stage shifts
Secondary	
To explore the efficacy of elinzanetant on sleep disturbance associated with menopause as determined by patient reported outcomes	Change from baseline in PROMIS SD SF 8b total score at week 4 Change from baseline in PROMIS SD SF 8b total score at week 4 Change from baseline in PROMIS SD SF 8b total score at week 12 Change from baseline in ISI total score at week 4 Change from baseline in ISI total score at week 12 Exploratory endpoints Change from baseline in subject-reported measures (as determined by the sleep diary (SD)) of sleep onset, duration, and continuity over time: sWASO, sLPS, sTST, sTIB, sSE, sNAW Change from baseline in proportion of days with participants rating "quite a bit" or "very much" sleep disturbance due to HF as measured by HFDD over time

rsion 2.0 Page: 11 of 57

To evaluate the safety of elinzanetant for the treatment of sleep disturbances associated with menopause	TEAEs Abnormal laboratory parameters

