4.1.2 Data Rules

Baseline: Unless otherwise specified, baseline is defined as the latest available valid measurement (including unscheduled measurements) on or before the start date of study treatment (for treated subjects) / randomization date (for randomized but not treated subjects). If the last observation available prior to randomization is the measurement from the screening visit, this would be used as the baseline value.

Change from baseline: To calculate the absolute change from baseline, the baseline value will be subtracted from the value under treatment/follow-up, i.e.,

Absolute change = post baseline value – baseline value.

Some parameters will be additionally analyzed as percent change defined as:

Percent change = [(post baseline value - baseline value) / baseline value] x 100.

Visit confirmation date for HF eligibility check: Refers to the date, as captured on the electronic handheld device, when the eligibility for inclusion criteria of ≥ 20 average weekly frequency of moderate to severe HFs was assessed.

Laboratory values <**X** or >**Y**: For laboratory values lower than a limit of detection X (reported as <X), half the value of X will be used for analysis (i.e., for values reported as "<X", "<X.XX", "<X.XX" or etc. the value for analysis will be derived by "X/2", "X.X/2", "X.XX/2", etc.).

Difference between 2 values <X will be assigned a value of 0. Ratio between 2 values <X will be assigned a value of 1.

For values which are higher than a limit of detection Y (reported as, >Y), the value of Y will be used for analysis.

Repeated measurements at the same date: For PROMIS SD SF 8b, ISI, GAD-7, PGI-S and PGI-C, if more than one entry on the same date for any pre- and post-baseline visit is available, then the first entry will be used and all observations will be presented in the data listings.

Start of treatment: Refers to the first drug intake and will be identified based on the 'Study Intervention' eCRF entry.

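### SAP 4.5.3.1 defines treatment-emergent laboratory abnormalities by a time window alone, so unchanged baseline abnormalities are counted and the arm contrast is diluted, mainly for non-liver parameters

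*SAP*

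**What the plan says.** The safety objective has two endpoints in both documents (SAP Table 1-1, Protocol Table 3-1): TEAEs and "Abnormal laboratory parameters". SAP 4.5.3.1 gives the incidence rule for the second: "The number of participants with treatment-emergent (i.e., 14 days from the last treatment intake) high or low abnormal laboratory values will be summarized", for each parameter and by arm, using scheduled and unscheduled values.

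For adverse events, SAP 4.5.2 asks for more than a window. It counts "AEs that occurred or worsened after the first dose of study intervention up to 14 days after the last dose of study intervention".

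A baseline value is available for every laboratory parameter. Under SAP 4.1.2, "baseline is defined as the latest available valid measurement (including unscheduled measurements) on or before the start date of study treatment". Safety blood samples are scheduled at SCR-1, T1 and T3/EoT (Protocol Table 1-2), so baseline will usually be the SCR-1 sample.

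Besides the count, SAP 4.5.3.1 plans this: "Continuous laboratory parameter values including the change from baseline will be summarized by visit and study treatment". SAP 4.5.3.2 adds, for ALT, AST, TB, ALP and INR, frequency tables of category at baseline and post-baseline. For ALT, AST, TB and ALP it also adds criteria expressed as multiples of baseline. Shift tables are specified for PGI-S (SAP 4.4.5) but not for laboratory data.

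**The concern.** The parenthesis in SAP 4.5.3.1 opens with i.e., so the window reads as the definition. It has an end and no stated start, and it does not ask whether the value was normal before treatment or has worsened. A woman with a high CK at SCR-1 and the same CK at Week 4 meets it.

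Eligibility lets such women in. Protocol 5.2, exclusion 5, removes ALT, AST and AP only above 2 x ULN, and exempts some raised bilirubin values ("TBL >ULN unless explained by Gilbert's syndrome") and raised INR when explained, for example by anticoagulants. Other analytes in Protocol Table 10-1, such as CK, LDH, lipids and HbA1c, have no numeric limit. They fall under exclusion 2: "Clinically significant abnormalities that interfere with the study goals, in the opinion of the investigator".

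Two things are at stake in a named endpoint. The absolute rate labelled treatment-emergent is too high, and both arms carry a common background that pulls their contrast toward no difference. Protocol Table 2-1 relies on CK, AST and LDH to evaluate skeletal muscle toxicity. AST has the liver tables. CK and LDH have no table that takes baseline category into account; SAP 4.5.3.2 mentions them only in listings.

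**Working it through.** The plan states no figure for laboratory abnormalities, so there is none to reproduce. The check is how the rule behaves under assumed rates.

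**Inputs.** Participants per arm: 39 (SAP Section 5). Not in the documents, therefore assumed:
- b, the share already abnormal at baseline in the same direction, 10% to 50%, equal in both arms;
- every baseline abnormality persists on treatment;
- p, new onset among women not abnormal at baseline, 10% on drug and 2% on placebo.

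**Formulas.**
- Tabulated share under the time-only rule = b + (1 − b) × p.
- Tabulated risk difference = (1 − b) × (p_drug − p_placebo).
- With a baseline condition and a matching denominator, the share is p in each arm whatever b is.

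**Results.**

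| b | Drug | Placebo | Ratio | Difference |
|---|---|---|---|---|
| 0% | 10.0% | 2.0% | 5.00 | 8.0 points |
| 10% | 0.10 + 0.90 × 0.10 = 19.0% | 0.10 + 0.90 × 0.02 = 11.8% | 1.61 | 7.2 points |
| 30% | 0.30 + 0.70 × 0.10 = 37.0% | 0.30 + 0.70 × 0.02 = 31.4% | 1.18 | 5.6 points |
| 50% | 0.50 + 0.50 × 0.10 = 55.0% | 0.50 + 0.50 × 0.02 = 51.0% | 1.08 | 4.0 points |

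The difference shrinks by the factor (1 − b); the ratio moves to 1 much faster. Neither reaches the null while b is below 100%.

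**Counts at b = 30%.** 0.30 × 39 = 11.7 women per arm are counted although nothing has emerged.

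**Chance imbalance at b = 30%.** The number of baseline-abnormal women differs between arms with standard deviation √(2 × 39 × 0.30 × 0.70) = √16.38 ≈ 4.0 women. The expected excess of new abnormalities on drug is 0.08 × 27.3 ≈ 2.2 women, where 27.3 = 0.70 × 39. Equal expected background therefore still leaves noise larger than the assumed signal.

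**Other assumed rates.** With new onset 20% against 5%, the true ratio is 4.0 and the difference 15 points. At b = 20% the table would show 36% against 24%, ratio 1.5, difference 12 points. If only 80% of baseline abnormalities persist, it would show 32% against 20%, ratio 1.6, difference again 12 points. The pattern is the same and the size depends on the inputs.

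**The case against.** The strongest reply is that the parenthesis cannot be a full definition, because it has no start. It may be shorthand for the end of the window in SAP 4.5.2, leaving emergent its usual meaning, and the table specifications sit in a separate document (SAP Section 1) that might add a baseline rule. This is fair as far as intent goes. It does not repair the text: the SAP writes out onset or worsening for adverse events, multiples of baseline for liver tests and shift tables for PGI-S, and writes none of these here.

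A reader might infer that the rule hides any new drug effect. The documents do not support that:
- The arithmetic shows dilution, not removal, and on the risk-difference scale the loss is modest when few women are abnormal at baseline. SAP 4.5.3.1 tabulates counts by arm, not ratios, in an estimation study without hypothesis tests (SAP Section 2).
- ALT, AST, TB, ALP and INR can be compared at baseline and post-baseline by arm in SAP 4.5.3.2, and all but INR have baseline-relative criteria. Most of the liver concern is answered there.
- Change from baseline is planned for continuous parameters. This stands, but a few new abnormalities among 39 women move a mean very little.
- Clinically significant laboratory changes must be recorded as adverse events (Protocol 8.3.3 and 10.3.1), and so reach the TEAE tables under a proper emergence rule. This stands for changes the investigator judges clinically significant.

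A reader might also infer that baseline abnormality outside the liver tests is unlimited. Exclusion 2 limits it by investigator judgement and covers clinical laboratory tests; what is missing is a numeric cut-off.

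**Conclusion.** The point holds in a limited form. As written, the rule counts unchanged baseline abnormalities as treatment-emergent. This overstates the absolute rate and dilutes the arm contrast in one of the two named safety endpoints. The weight falls on non-liver parameters, CK and LDH above all.

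The size cannot be fixed from the documents. Under the assumed 10% against 2%, with full persistence and a baseline-abnormal share of 10% to 50%, the risk difference falls from 8 points to between 7.2 and 4.0, and the ratio from 5 to between 1.61 and 1.08. Lower baseline shares or less persistence would reduce the effect. If the separate table specifications already apply a baseline condition, what remains is a mismatch with the SAP text.

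**What to change.** In SAP 4.5.3.1, define a treatment-emergent high (low) as a value above (below) the reference range, after first dose and up to 14 days after last dose, in a participant whose baseline was not already high (low). Use as denominator the participants with such a baseline and at least one post-baseline value.

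That sentence alone is not enough. It takes women already abnormal at baseline out of both numerator and denominator, so a mildly raised CK that climbs steeply would vanish from the count. Add shift tables from baseline to worst post-baseline value (low, normal, high) by arm. A move within the high category does not show in such a table, so for CK and LDH also give the maximum multiple of ULN by baseline category.

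The cost is one SAP sentence and a few more tables. Baseline is already derived for change from baseline, and no new data are needed. The drawback is that denominators will differ between parameters and must be shown.
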